5.4 Treatments

5.4.1 Identity of investigational product(s)

Investigational product	Dosage form and strength	Manufacturer
Ticagrelor	90 mg film coated tablet – BID	AstraZeneca

Clopidogrel	75 mg film coated tablet – QD	To be defined (PIs decide which clopidogrel will be used)
	300 mg film coated tablet – QD	

Ticagrelor

Chemical name (IUPAC): (1S,2S,3R,5S)-3-[7-[[[(1R,2S)-2-(3,4-difluorophenyl)cyclopropyl]amino]-5-(propylthio)3H-[1,2,3]triazolo[4,5-d]pyrimidin-3-yl]-5-(2-hydroxyethoxy)cyclopentane-1,2-diol Laboratory code: AZD6140 (previously AR-C126532XX)

Chemical structure

Ticagrelor has 6 asymmetric carbon atoms, all of which are prepared by synthesis. All stereocentres are introduced by stereo-selective chemistry early in the synthetic pathway where correct configuration is established.

Molecular formula: C₂₃H₂₈F₂N₆O₄S

Relative molecular mass: 522.57

Partition coefficient, log P (octanol/water): >4.0

General properties

Ticagrelor is a crystalline powder with an aqueous solubility of approximately 10 µg/mL at room temperature. During routine manufacture solid ticagrelor is only isolated as a single polymorph, which has been used in all toxicological and clinical studies to date.

Drug product

Presentation

Ticagrelor will be provided as Brilique tablets. The drug product is a conventional immediate release (IR) tablet for oral use. One tablet strength will be available: 90 mg tablets - presented as round, biconvex, yellow, film coated tablets

Composition

The composition of the ticagrelor tablet core is ticagrelor, mannitol, dibasic calcium phosphate, sodium starch glycolate, hydroxypropyl cellulose, and magnesium stearate. The composition of the tablet coating is: hydroxypropyl methylcellulose, titanium dioxide, talc, polyethylene glycol 400, and iron oxide yellow (45 mg and 90 mg tablet strengths); and hydroxypropyl methylcellulose, titanium dioxide, talc and polyethylene glycol 400 (60 mg tablet strength).

Clopidogrel

Clopidogrel is a thienopyridine class inhibitor of P₂Y₁₂ ADP platelet receptors. Chemically it is methyl (+)-(S)-α-(2-chlorophenyl)-6,7-dihydrothieno[3,2-c]pyridine-5(4H) acetate sulfate (1:1). The empirical formula of clopidogrel bisulfate is C₁₆H₁₆ClNO₂S•H₂SO₄ and its molecular weight is 419.9.

Clopidogrel will be provided as Plavix 75mg tablets or equivalent according to local availability.

5.4.2 Doses and treatment regimens

For the ticagrelor group: loading dose 180 mg ticagrelor (2×90mg tablets). Thereafter, 90mg (1 tablet) b.i.d. At the end of the study period, treatment should be continued according to the prescription of the investigator and the attending physician.

For the clopidogrel group: Patients not on clopidogrel - loading dose 300 mg clopidogrel (4×75mg tablets). At the time of PCI an additional 75 mg dose. Thereafter, 75mg o.d. Patients already on clopidogrel – continuation of maintenance dose. At the end of the study period, treatment should be continued according to the prescription of the investigator and the attending physician.

5.4.3 Additional study drug

Ticagrelor or clopidogrel will be given as part of dual antiplatelet treatment in combination with aspirin at an initial loading dose of 150-300mg (according to primary investigator preference) and 100mg maintenance dose thereafter.

5.4.4 Labeling

Packaging and labelling procedures for the study medication will be followed according to the local regulatory requirements and regulations for interventional studies.

5.4.5 Storage

The product should be stored in the pack provided and used according to the instructions on the label.

5.5 Concomitant and post-study treatment(s)

All medications taken by the patient during the treatment period in addition to the study medication, are termed concomitant medication. All concomitant medication taken during the treatment period of the study will be documented on the case report form (trade name, start and stop date and daily dose). Concomitant medication must also be recorded in the patient's records. All prior medications administered within 1 week of enrolment into the study must be documented on the case report form.

5.6 Treatment compliance

Inpatient administration will be documented (date, time, dose, and signature of dispensing person). A patient diary will be used to document outpatient administration. Drug accountability of the unused study medication will be performed. The treatment compliance should be between 80% and 120%.

5.6.1 Accountability

Each patient will be dispensed sufficient medication for one month of therapy. Upon dispensation, the investigator must write the following in the Investigational Product Dispensing Log: subject ID and initials and date dispensed, the total dose given

weekly/monthly and frequency of dosage, total bottles dispensed, batch number and expiry date of product.

The investigator or designee must maintain current and accurate record of the receipt, inventory and dispensing, including shipping invoices, of all study supplies. The Investigational Product Accountability Log must include:

- Date received
- Delivery order (D.O.#) reference number and amount received and placed in storage
- Name of study medication and dosage
- Amount currently in storage area
- Label ID number or batch number/Lot number
- Name and initial of person responsible for each investigational product inventory entry/movement
- Amount dispensed to and returned by each subject, including unique subject identifiers
- Amount transferred to another area for dispensing or storage
- Non-study disposition (eg. Lost, wasted, broken)
- Amount returned to sponsor
- Amount destroyed at study site ID number or batch number/Lot number

5.7 Discontinuation of investigational product

Patients who require discontinuation of ticagrelor are at increased risk for cardiac events. Premature discontinuation of treatment should be avoided. If ticagrelor must be temporarily stopped due to an adverse event(s), it should be re-initiated as soon as possible when the benefits outweigh the risks of the adverse event or when the adverse event has come to resolution.

5.7.1 Procedures for discontinuation of a subject from investigational product

Patients who require discontinuation of ticagrelor should receive dual antiplatelet treatment for a period, which is defined by disease presentation (stable CAD or NSTEMI-ACS) and type of stent (or stents) used during PCI. The investigator and the subjects' physicians should base the decision for ticagrelor discontinuation, switch to clopidogrel, and required loading doses on relevant clinical practice guidelines and established local clinical practice.²³

Subjects who discontinue the investigational product should:

- Have the reason(s) for discontinuation recorded
- Be asked about the presence of any AEs and if so should be followed up by regular scheduled visits, telephone contact, correspondence or home visits until satisfactory clinical resolution of AEs is achieved.

- Be seen by an investigator and all final assessments will be performed and recorded in the termination page of CRF.
- Have at least one follow-up contact for safety evaluation during the 30 days following the last dose of study treatment.
- In the event of pregnancy, the subject should be monitored until conclusion of the pregnancy and the outcome of pregnancy reported.
- Have study treatment returned (following previously described accountability practices)

5.8 Withdrawal from study

Subjects have the right to withdraw from the study at any time for any reason, including personal reasons. The Investigator also has the right to withdraw subjects from the study in the event of:

- An adverse event which is considered intolerable by the subject or the Investigator and to interfere with the continuation of the survey or the subject evaluation.
- An abnormal laboratory test result which is considered clinically significant by the Investigator and possibly interfering with the continuation of the survey or the subject evaluation.
- The development of an exclusion criterion.

It is understood by all concerned Investigators that an excessive rate of withdrawals can render the study uninterpretable; therefore, unnecessary withdrawals of subjects should be avoided.

However, should a subject definitely decide to withdraw, all efforts will be made by the Investigator to complete and report the final observations as thoroughly as possible. A complete final evaluation at the time of the withdrawal will be performed with an explanation of the exact reason why the subject is withdrawing from the study in the “Study Completion Summary” of the CRF.

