3. STUDY PLAN AND PROCEDURES

3.1 Overall study design and flow chart

The TRIP study will be a randomized, assessor-blind, active comparator-controlled, clinical trial using a 2×2 factorial design, with 1:1 patient allocation to ticagrelor or clopidogrel and within each treatment a 1:1 allocation to RIPC or control.

According to the study plan, patients who are referred for coronary angiography or NSTEMI-ACS may be screened for randomization.

	Day 1/ Screening	Day 2	Day 3	Day 30 (±5days)
Informed consent form	x			
Inclusion criteria	x			
Exclusion criteria	x	x	x	

Medical history	X			X
Concomitant disease	X			X
Concomitant medication	X	X	X	X
Physical examination (vital signs)	X	X	X	X
ECG	X	X		
Local laboratory values	X	X	X	
Randomization	X	X		
Treatment initiation	X			
RIPC		X		
Coronary angiography assessment		X		
PCI		X		

[figure not shown]
Day 1 of the study is defined as the day of randomization to ticagrelor versus clopidogrel. This should be chosen by the investigator to be the day before the scheduled PCI procedure.

Day 2 of the study is defined as the day of randomization to RIPC or control and subsequent (within 1 hour) coronary angiography and PCI.

In patients already treated with clopidogrel for 3 to 7 days, actions performed on Day 1 and Day 2 may be combined into a single day provided that;

- a. Twenty four hours have elapsed between the last dose of clopidogrel and the randomization to the ticagrelor or clopidogrel group, and
- b. There is sufficient time (2-4 hours) between the randomization and subsequent intake of clopidogrel or ticagrelor and the 2nd randomization to the RIPC or control group.

If for unforeseen reasons, PCI is not conducted within the prespecified timeframe the patient should be withdrawn from the study.

* In case of a patient already on clopidogrel for 3-7 days, ticagrelor loading dose is administered on the day of the procedure (24 hours after the last clopidogrel dose), and no 2nd ticagrelor dose is administered. ** In case of a patient already on clopidogrel for 3-7 days, no loading dose of clopidogrel is administered, but the patient ideally receives 75mg clopidogrel 2-3 hours before the procedure.

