4.2 Exclusion criteria

Subjects should not enter the study if any of the following exclusion criteria are fulfilled:

1. Women of childbearing potential
2. Severe comorbidity (estimated life expectancy <6 months)
3. Baseline cTnI before PCI that is not stable or falling or is $> 5 \times 99^{\text{th}}$ percentile URL.
4. End-stage renal disease(eGFR<15 ml/min/1.73 m²)
5. CRUSADE Bleeding Score >50
6. Patients with an indication for oral anticoagulation
7. On maintenance therapy with ticagrelor or those that have received clopidogrel for less than 3 days
8. Use of nicorandil or glibenclamide
9. Concomitant theophylline/aminophylline use
 - I. Known contraindications to the use of ticagrelor Hypersensitivity to the active substance or to any of the excipients
 - II. Active pathological bleeding
 - III. History of intracranial haemorrhage
 - IV. Moderate to severe hepatic impairment
 - V. Co-administration of ticagrelor with strong CYP3A4 inhibitors (e.g., ketoconazole, clarithromycin, nefazodone, ritonavir, and atazanavir).

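### Exclusion criteria are re-checked after drug randomisation and can end study participation, so dosed patients can leave the primary analysis for reasons, notably bleeding, that the drug may affect

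*Combined protocol and SAP*

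**What the plan says.** The schedule in section 3.1 has the columns "Day 1/ Screening Day 2 Day 3 Day 30 (±5days" and, under them, the row "Exclusion criteria x x x". Inclusion criteria carry one mark only. The same section states: "Day 1 of the study is defined as the day of randomization to ticagrelor versus clopidogrel". Treatment initiation is also marked on Day 1.

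Section 5.8 reads: "The Investigator also has the right to withdraw subjects from the study in the event of" several circumstances, the last being "The development of an exclusion criterion". The other two are an intolerable adverse event and a clinically significant laboratory abnormality. This is withdrawal from the study. Stopping the drug is dealt with separately in section 5.7.

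The exclusion list in section 4.2 includes "Active pathological bleeding" and "Baseline cTnI before PCI that is not stable or falling" (or above five times the 99th percentile limit). Section 6.2 re-examines for bleeding and re-measures cTnI on Day 2 before the procedure. Section 5.3 makes the trial open label, with blinded reading of the ST-segment only.

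Section 12.2 analyses efficacy in the safety set (at least one dose) by ANCOVA of 24 h cTnI on drug, RIPC and pre-procedural cTnI. It gives no rule for a missing 24 h value. The per-protocol set in 12.1.1 requires a valid 24 h sample.

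**The concern.** A comparison by randomised drug is protected only while patients stay in it whatever happens after randomisation. Here a check made after dosing, by someone who knows the drug, can remove a patient because of an event the drug may have caused. If that happens more often in one arm, and those patients differ in troponin from the rest, the drug effect is estimated in a selected remainder. The error can go either way. The 15% dropout allowance in section 12.3 protects precision and does nothing about selection.

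The same route touches the safety comparison: a patient withdrawn after a bleed may miss the scheduled Day 30 examination, so a later or worsening bleed could go unseen.

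**Working it through.** **1. Do the marks mean Days 1, 2 and 3?** The table was read from a PDF, so I checked rows against the text. Laboratory values also carry three marks, and section 6.4.4 confirms Days 1, 2 and 3. ECG carries two, and section 6.4.6.1 confirms Days 1 and 2. Marks therefore fill from the left, and the second and third exclusion checks follow randomisation and dosing.

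**2. Which criteria can act, and when?**
- Bleeding: can newly arise on Day 2 or Day 3. Section 1.4 links it to the more potent drug.
- Pre-PCI cTnI: defined before PCI, so it can act on Day 2 but not through values drawn on Day 3. The documents show no drug effect on it; the hypothesis in 1.2 concerns release after the procedure.

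Patients already on clopidogrel have one combined screening and pre-procedural assessment (section 6.2), so the Day 2 route is narrower for them.

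**3. What happens to the data?** Membership of the safety set needs one dose, but the ANCOVA needs an outcome. With no 24 h value and no missing-data rule, the patient drops out of the fit.

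**4. The plan's own figure.** Inputs from section 12.3: cell means 0.08 and 0.14 ng/mL (ticagrelor, with and without RIPC), 0.12 and 0.24 (clopidogrel), SD 0.20, correlation 0.7, 80% power, α 0.05.
- Drug effect: (0.12 + 0.24)/2 − (0.08 + 0.14)/2 = 0.18 − 0.11 = 0.07 ng/mL.
- Adjusted SD: 0.20 × √(1 − 0.7²) = 0.143.
- This needs 66 per drug arm, 132 in total; 132 × 1.15 = 151.8, matching 152. (132/0.85 would give 156.)

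A four-group test with unadjusted SD also gives 132, so the plan does not show which route was used. I use 0.07 only as a yardstick.

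**5. Size, by illustration.** The retained mean in an arm differs from its full mean by (share withdrawn) × (withdrawn minus retained mean), with sign reversed. With the same mean difference in both arms, the drug effect moves by (difference in withdrawal share) × (mean difference). The inputs below are assumptions, not document figures, and the cTnI difference is what remains after baseline adjustment.

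| Withdrawal difference | cTnI difference (ng/mL) | Shift (ng/mL) | Share of 0.07 |
|---|---|---|---|
| 3 points | 0.1 | 0.003 | 4% |
| 3 points | 0.2 | 0.006 | 9% |
| 10 points | 0.1 | 0.010 | 14% |
| 10 points | 0.2 | 0.020 | 29% |

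For scale, 10 points is 0.10 × 76 = 7.6 patients in a drug arm, against a planned loss from all causes of 0.15 × 76 = 11.4. The upper row is therefore severe for a single reason.

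**6. The troponin route under the planned model.** Suppose the top 10% by baseline cTnI are removed from the clopidogrel arm only. With normal data the baseline mean of those left falls by 0.1755/0.90 = 0.195 SD, so the unadjusted outcome mean falls by 0.7 × 0.20 × 0.195 = 0.027, and the unadjusted difference drops from 0.070 to 0.043. A simulation of one-arm removal of the top 10% by baseline gave the same 0.043 unadjusted, but an ANCOVA estimate still at 0.070, because baseline is the covariate.

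**The case against.** The strongest reply has five parts.

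- *The troponin criterion does little harm.* This stands for selection on baseline level, as step 6 shows. A reader might infer that patients are being removed on the outcome marker itself. The criterion is a pre-PCI value, it is in the model, and no drug effect on it is documented. Selection on a rising trend would be only partly absorbed.
- *Withdrawal is a right, not a duty, and section 5.8 says unnecessary withdrawals are to be avoided.* True, and section 1.4 expects bleeding to be minor. The rule still permits the loss, at unblinded discretion.
- *Bleeding data are mostly kept.* Largely true. The triggering bleed is counted, and section 5.2 gives withdrawn dosed patients follow-up of adverse events to resolution, final assessments and at least one contact within 30 days of the last dose. A reader might infer that bleeding outcomes are lost in those who bled; the documents support only that scheduled follow-up may be shortened.
- *The RIPC comparison is largely untouched by Day 2.* True: the second randomisation comes after the Day 2 pre-procedural assessment, so a check before it is ordinary eligibility for that factor.
- *Deleting one bullet does not close the door.* Correct. The adverse-event and laboratory grounds in 5.8 permit the same losses, and sections 3.1 and 5.1 separately withdraw patients whose PCI is not done in time. If PCI does not take place there is no 24 h value to recover. The fix has to address these points.

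**Conclusion.** The point holds as a design weakness in the drug comparison. Eligibility is re-applied after dosing, study withdrawal is permitted on that basis by someone who knows the drug, and at least one criterion, active bleeding, is something the plan expects the drug to influence. A withdrawn patient without a 24 h sample is lost to the primary ANCOVA.

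The size is unknown. The range of 0.003 to 0.020 ng/mL rests wholly on assumed withdrawal and troponin differences. A reader might go further and infer a large fall in power by subtracting these shifts from 0.07 and applying the adjusted SD. The documents do not support that: they give no withdrawal rates by arm, the shift could equally exaggerate the effect, and on the baseline-troponin route the unadjusted shift does not carry into the adjusted analysis.

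**What to change.** 1. In section 3.1, remove the Day 3 mark for exclusion criteria. A Day 2 check may inform care but should not end follow-up.
2. In section 5.8, delete the bullet on developing an exclusion criterion, and state that eligibility is fixed at drug randomisation for follow-up and analysis.
3. State that the remaining investigator-initiated grounds in 5.8 (adverse event, laboratory result) end study follow-up only if the patient withdraws consent. Such patients have the 24 h cTnI where PCI was done and the Day 30 assessment, and are analysed as randomised.
4. Reconcile this with the rule in sections 3.1 and 5.1 on PCI outside the timeframe, so that those patients at least keep the Day 30 bleeding follow-up.
5. Add a sensitivity analysis without patients whose pre-PCI cTnI was unstable.

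Treatment decisions stay with the clinicians under section 5.7 and are not affected. The cost is a few lines of wording; the 24 h sample and Day 30 visit are already scheduled. The downside is some added noise from a few patients with unstable baseline troponin, which item 5 makes visible. Patients who never have PCI will still lack a 24 h value.

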6. COLLECTION OF STUDY VARIABLES

6.1 Recording of data

Data collection and recording will be performed through paper case report forms (pCRFs) that will be provided by the Sponsor to the participating site for each subject separately. The use of a waterproof ballpoint black pen is recommended for the record of data on the pCRF. The investigator should record all relevant data in the appropriate CRF and should ensure the accuracy, completeness, legibility and timeliness of the data reported to the sponsor in the CRFs and in all required reports. Accurate and reliable data collection will be assured by verification and cross-check of 100% of the CRFs against the investigator's records (source document verification).

6.2 Data collection at enrolment and follow-up

Screening (in most cases expected to be the same day with first randomization-Day1)

During this period the investigator will evaluate and record

- Indication for coronary angiography or PCI (stable CAD, NSTEMI-ACS)
- Demographics (age, gender, height, weight, body mass index)
- History of risk factors for cardiovascular disease (Diabetes mellitus, dyslipidemia, hypertension, smoking)
- Medical history including history of previous MI, previous PCI, previous CABG, New York Heart Association Class, Canadian Cardiology Society Angina Class
- Prior and concomitant medication
- Physical examination with vital signs (heart rate, blood pressure)
- Electrocardiogram
- Local laboratory values (hemoglobin, complete blood count including platelet count, serum creatinine, AST, ALT, INR, cardiac Troponin I)

Day 2 - Pre-procedural assessment

- Physical examination with vital signs (heart rate, blood pressure). At this time signs and symptoms of bleeding should be specifically examined.
- Local laboratory values (hemoglobin, complete blood count including platelet count, serum creatinine, AST, ALT, INR, cardiac Troponin I)

In the case of patients already on clopidogrel there will be one combined assessment for screening and pre-procedurally.

Day 2 - Preconditioning

- The timing of the last cycle of RIPC in relation to subsequent PCI should be specifically recorded

Day 2 - Peri-procedural

- Angiographic parameters (number of diseased vessels, target vessel, jeopardy score, rentrop score, American heart association lesion type, stenosis severity, acute gain, timi flow score)
- Procedural parameters (access site, stent length, type of stent used, screen time, radiation dose, contrast dose, number of predilations, predilation time, number of postdilations, postdilation time)
- Complications (jailed side branch, dissection)
- ST-segment deviation during balloon occlusion will be monitored as a secondary efficacy variable. It will be defined as the absolute value of ST-segment deviation at 60-80ms after the J-point in mm at the beginning of coronary angiography minus ST-segment deviation at 60-80ms after the J-point in mm during balloon occlusion.

Day 2 - Post-procedural

- Physical examination with vital signs (heart rate, blood pressure). At this time signs and symptoms of access site bleeding should be specifically examined.
- Electrocardiogram
- Chest pain during PCI will be assessed during the post-PCI clinical examination of the subject by the investigator or by an appropriately qualified person to whom the investigator has delegated this duty. A numerical 10 point scale will be used (0: no pain, 10: most severe discomfort ever experienced)

Day 3

- Physical examination with vital signs (heart rate, blood pressure). At this time signs and symptoms of access site bleeding should be specifically examined.
- Local laboratory values, i.e. hemoglobin, complete blood count including platelet count, serum creatinine, AST, ALT, INR, and Cardiac troponin I at 24 hours post-PCI

Day 4-day 29 (Follow-up)

- Physical examination with vital signs (heart rate, blood pressure), while admitted in the hospital. After discharge the patients will be instructed to inform the investigator for potential adverse events.

Day 30 Follow-up visit

- Physical examination with vital signs (heart rate, blood pressure). Signs and symptoms of bleeding should be specifically examined.

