2.3 Safety objective

Safety monitoring will be performed daily during the index hospitalization. The presence of adverse events will be assessed by history, detailed physical examination and appropriate laboratory tests that will be described in the protocol accordingly.

In addition patients will be instructed to contact the study personnel in case of any emergency situation whereas an adverse event reporting system will be available throughout the study.

In detail, bleeding according to the Thrombolysis in Myocardial Infarction (TIMI) bleeding criteria will be recorded and assessed throughout study duration. According to these criteria bleeding is defined as follows:

Non-CABG Related Bleeding:

1. Major

- Any intracranial bleeding (excluding microhemorrhages <10 mm evident only on gradient-echo MRI)
- Clinically overt signs of hemorrhage associated with a drop in hemoglobin of ≥ 5 g/dL or a $\geq 15\%$ absolute decrease in haematocrit
- Fatal bleeding (bleeding that directly results in death within 7 d)

2. Minor

- Clinically overt (including imaging), resulting in hemoglobin drop of 3 to <5 g/dL or $\geq 10\%$ decrease in haematocrit
- No observed blood loss: ≥ 4 g/dL decrease in the haemoglobin concentration or $\geq 12\%$ decrease in haematocrit

- Any overt sign of hemorrhage that meets one of the following criteria and does not meet criteria for a major or minor bleeding event, as defined above
- Requiring intervention (medical practitioner-guided medical or surgical treatment to stop or treat bleeding, including temporarily or permanently discontinuing or changing the dose of a medication or study drug)
- Leading to or prolonging hospitalization
- Prompting evaluation (leading to an unscheduled visit to a healthcare professional and diagnostic testing, either laboratory or imaging)

3. Minimal

- Any overt bleeding event that does not meet the criteria above
- Any clinically overt sign of haemorrhage (including imaging) associated with a <3 g/dL decrease in haemoglobin concentration or <9% decrease in haematocrit

Bleeding in the Setting of CABG:

- Fatal bleeding (bleeding that directly results in death)
- Perioperative intracranial bleeding
- Reoperation after closure of the sternotomy incision for the purpose of controlling bleeding
- Transfusion of ≥ 5 U PRBCs or whole blood within a 48-h period; cell saver transfusion will not be counted in calculations of blood products.
- Chest tube output >2 L within a 24-h period

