It is important to distinguish between serious and severe AEs. Severity is a measure of intensity whereas seriousness is defined by the criteria in Section 6.4.2. An AE of severe intensity need not necessarily be considered serious. For example, nausea that persists for several hours may be considered severe nausea, but not a SAE. On the other hand, a stroke that results in only a limited degree of disability may be considered a mild stroke but would be a SAE.

The Sponsor or its designee will classify events using Medical Dictionary for Regulatory Activities (MedDRA).

Causality collection

The Investigator will assess causal relationship between Investigational Product and each Adverse Event, and answer ‘yes’ or ‘no’ to the question ‘Do you consider that there is a reasonable possibility that the event may have been caused by the investigational product?’.

For SAEs causal relationship will also be assessed for other medication and study procedures. Note that for SAEs that could be associated with any study procedure the causal relationship is implied as ‘yes’.

Adverse Events based on signs and symptoms

All AEs spontaneously reported by the subject or reported in response to the open question from the study personnel: <<‘Have you had any health problems since you were last asked?’>> or revealed by observation will be collected and recorded in the CRF. When collecting AEs, the recording of diagnoses is preferred (when possible) to recording a list of signs and symptoms. However, if a diagnosis is known and there are other signs or symptoms that are not generally part of the diagnosis, the diagnosis and each sign or symptom will be recorded separately.

Adverse Events based on examinations and tests

The results from protocol mandated laboratory tests and vital signs will be summarized in the clinical study report. Deterioration as compared to baseline in protocol-mandated laboratory values and vital signs should therefore only be reported as AEs if they fulfil any of the SAE criteria or are the reason for discontinuation of treatment with the investigational product.

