12.2 Methods of statistical analyses

The efficacy analysis will be performed in the population of subjects valid for safety analysis.

The statistical assessment of the primary outcome measure (post-procedural cTnI) will be performed using ANCOVA (analysis of covariance), with post-procedural cTnI as a dependent variable, -ticagrelor/clopidogrel treatment and –RIPC/no RIPC as fixed factors and pre-procedural cTnI as a covariate. If not mentioned otherwise, all statistical tests will be performed tow-sided with a type I error rate of 5% and 95% confidence intervals (two-sided) will be given.

The statistical assessment of the secondary outcome measures (pain score, and ST-segment deviation) will be performed using ANOVA (analysis of variance). The ANOVA tests the null hypothesis that samples in two or more groups are drawn from populations with the same mean values. If the ANOVA test is statistically significant, pairwise comparison of subgroups will be performed with the Tukey-Kramer test. If not mentioned otherwise, all statistical tests will be performed tow-sided with a type I error rate of 5% and 95% confidence intervals (two-sided) will be given.

The safety analysis will be performed in the population of subjects valid for safety analysis.

The incidence of the composite of major and non-major bleeding according to the TIMI criteria and the incidence of major bleeding will be tabulated and further analyzed using Fisher's exact test. Fisher's exact test is a significance test for a 2x2 table. This test evaluates all distribution probabilities for a 2 x 2 table and produces an exact probability for a given set of observed frequencies. The null hypothesis is that the row and column variables are unrelated, or that there is no difference in the respective proportions. If not mentioned otherwise, all statistical tests will be performed two-sided with a type I error rate of 5% and 95% confidence intervals (two-sided) will be given.

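### After discharge, resolved minor and minimal bleeds depend on patient-initiated reports or unaided recall at Day 30, so the tested bleeding composite may miss some of them, possibly unevenly by open-label arm

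*Combined protocol and SAP*

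**What the plan says.** Section 2.3 sets the aim: "bleeding according to the Thrombolysis in Myocardial Infarction (TIMI) bleeding criteria will be recorded and assessed throughout study duration". Its lowest category, minimal bleeding, includes "Any overt bleeding event that does not meet the criteria above". Section 12.2 defines what is analysed: "The incidence of the composite of major and non-major bleeding according to the TIMI criteria and the incidence of major bleeding will be tabulated", followed by Fisher's exact test, two-sided at 5%.

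The means of capture differ by period.

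- **In hospital.** Section 6.2 directs attention to bleeding before the procedure, after it and on Day 3. Sections 6.4.4 and 6.4.5 give haemoglobin on Days 1 to 3 and daily examination until discharge.
- **Discharge to Day 29.** Section 6.2 says "After discharge the patients will be instructed to inform the investigator for potential adverse events". Section 2.3 adds that "patients will be instructed to contact the study personnel in case of any emergency situation" and that an adverse event reporting system is available. The schedule in section 3.1 has no visit or call between Day 3 and Day 30.
- **Day 30.** Section 6.2 says "Signs and symptoms of bleeding should be specifically examined". Section 3.1 lists a medical history at this visit, and section 6.4.8 directs examinations after PCI towards symptoms and signs of bleeding. Under section 6.4.3, adverse events come from spontaneous report, from observation, or are "reported in response to the open question from the study personnel"; that question is a general one about health problems.

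Section 5.6 already gives patients a diary, for dosing: "A patient diary will be used to document outpatient administration". Section 5.3 makes the drugs open label. It describes blinded assessment in detail only for ST-segment deviation.

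**The concern.** The composite counts patients with any TIMI bleed. On the natural reading, non-major includes minimal, although section 12.2 does not list the categories. A nosebleed or bruise on Day 10 may leave nothing to see on Day 30. It becomes an event only if the patient called about it or recalls it up to three weeks later. Section 1.4 expects the extra bleeding from the more potent drug to be minor and not life-threatening, and this is the kind that such a method captures least well.

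Two things are at stake. Equal under-capture in both arms lowers the power of the bleeding comparison. Unequal capture, which is possible because patients know their drug, moves the observed risk ratio in whichever direction the reporting leans. Blinded grading would correct neither, because a bleed that was never reported cannot be graded.

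**Working it through.** **Inputs from the protocol.** N = 152 with 1:1 allocation to drug, so 76 v 76; Fisher's exact test, two-sided, α = 0.05. I take the 2×2 table to be ticagrelor v clopidogrel, which section 12.2 does not spell out. The safety set needs only one dose, so all 152 can count.

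**The plan's own figure.** No bleeding rate or bleeding power is stated. N = 152 rests on troponin and serves here only as the denominator. It reproduces for the drug main effect:

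- Difference: (0.12 + 0.24)/2 − (0.08 + 0.14)/2 = 0.07.
- SD after adjustment: 0.20 × √(1 − 0.7²) = 0.143.
- n per arm: 2 × [0.143 × (1.96 + 0.842)/0.07]² ≈ 65.4, rounded up to 66, so 132 in total.
- With 15% dropout: 132 × 1.15 = 151.8, rounded up to 152. (132/0.85 would give 156; this point does not contest N.)

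**Assumptions, none of them in the documents.** Let p be an arm's true 30-day proportion with any bleed, h the share of bleeds before discharge (all captured), and c the capture fraction after discharge. Then

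observed proportion = p × [h + (1 − h) × c].

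Rejection probabilities come from exact enumeration of all 77 × 77 outcomes. In the tables, h = 0.5 is the main illustration and h = 0 is the extreme in which every bleed occurs after discharge.

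**Equal capture, true 25% v 10%**

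| Post-discharge capture | Observed, h = 0.5 | Power | Observed, h = 0 | Power |
|---|---|---|---|---|
| 100% | 25% v 10% | 62% | 25% v 10% | 62% |
| 80% | 22.5% v 9% | 56% | 20% v 8% | 49% |
| 60% | 20% v 8% | 49% | 15% v 6% | 35% |

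Example: 25% × (0.5 + 0.5 × 0.8) = 22.5%.

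**Unequal capture, true 20% in both arms**

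| Capture, arm A v arm B | Observed, h = 0.5 | Rejection | Observed, h = 0 | Rejection |
|---|---|---|---|---|
| 100% v 100% | 20% v 20% | 3.1% | 20% v 20% | 3.1% |
| 90% v 60% | 19% v 16% | 5.0% | 18% v 12% | 13% |
| 90% v 50% | 19% v 15% | 6.6% | 18% v 10% | 22% |

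Example: 20% × (0.5 + 0.5 × 0.6) = 16%. The two-sided rejection rate is the same whichever arm reports more. Fisher's test is conservative (3.1% against a nominal 5%), and this absorbs the first of the two unequal-capture cases.

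**The case against.** The strongest reply is that bleeding enquiry at Day 30 is already planned. Section 6.2 asks for symptoms as well as signs, and symptoms are normally elicited by asking. Sections 3.1 and 6.4.8 point the same way. A reader might infer that bleeding is asked about only through the general health question of section 6.4.3; the documents do not support that. Serious bleeds would also surface as serious adverse events. What remains is that the enquiry has no stated wording or recall period, and nothing recorded at the time to prompt it. The case report form and the diary are not among the documents, so they may hold more than the protocol states.

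Second, in-hospital bleeds, including those at the access site, are checked closely. The capture loss cannot be applied to all 30-day bleeds, and this stands in full. It is why the h = 0 columns are an extreme and not the estimate.

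Third, nothing says which arm would report more readily, and an unblinded patient can over- or under-report in a diary too. This also stands: the remedy reduces the problem without removing it.

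Fourth, bleeding is a safety variable for which the trial was not sized, and patient reports plus a Day 30 visit are a workable 30-day safety plan. That limits the weight of the point but does not answer it, since section 12.2 does test the composite.

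**Conclusion.** The point holds as an improvement to make, not as a serious flaw. After discharge, a minor or minimal bleed that has resolved reaches the data only through a patient-initiated report or through recall at one visit. That visit is directed at bleeding but is not standardised. Because the composite includes non-major bleeds, some events may be missed, and possibly unevenly by arm.

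The size is illustrative. If half of bleeds occur before discharge and are all captured, power for 25% v 10% falls by about 6 to 13 percentage points at 80% to 60% post-discharge capture. False rejection at 20% in both arms rises from 3.1% to 5.0% or 6.6%. Bleeding rates, capture fractions and the split at discharge are all assumptions.

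Two stronger readings should be resisted. A reader might infer a false-positive rate as high as 22%; that requires essentially all bleeds to occur after discharge, which the documents do not suggest. A reader might also infer a bias against ticagrelor; the documents give no direction. The primary endpoint, troponin at 24 hours, is unaffected.

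**What to change.** Add a bleeding entry to the outpatient diary of section 5.6: none, type of bleed, and whether care was sought. The last item supplies what section 2.3 needs for grading, since it classifies bleeds partly by intervention and unscheduled visits.

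In the Day 30 part of section 6.2, state that every patient in both arms is asked the same fixed bleeding questions, covering the TIMI categories since discharge and with the diary at hand. In section 12.2, state that non-major includes minimal, if that is intended.

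This needs no new visit, staff or sample. The costs are one diary line, a short question list, slight patient burden and more trivial bleeds recorded, which the definition in section 2.3 already counts. Some open-label reporting bias will remain and should be acknowledged when the bleeding results are reported.
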